11.10 Efficacy Analyses

11.10.1Primary Efficacy Analyses

The primary endpoints will be assessed in the Efficacy population, overall and separately for patients with mBCC and patients with locally advanced BCC.

The objective response rate (ORR) will be calculated as the number of patients satisfying the OR criteria divided by the number of subjects in the Efficacy population. Patients without at least one post-baseline response assessment will be treated as non-responders. Further, patients who experience progressive disease but continue treatment under the protocol and experience partial or complete response in a subsequent tumor assessment, will be considered partial or complete responders. A continuity-corrected 95% confidence interval based on the normal approximation will accompany each ORR.

Complete response rates (CRR) will be summarized in parallel fashion to ORR.

11.10.20ther Efficacy Analyses

PFS will be analyzed using the Kaplan-Meier method in the Efficacy population, separately for patients with mBCC and patients with locally advanced BCC.

Summary statistics from the Kaplan-Meier distribution will be determined, including the median and estimates at 3, 6, 9, 12 months. These statistics will be provided as point estimates with 95% confidence intervals.

DOR summary will include at least median (in months), range and patients (n, %) with observed DOR for at least 6 months.

DSD summary will include at least median, range, min, max and patients (n, %) with observed SD for at least 6 months.

DCR summary will include at least median, range, min, max and patients (n, %) with observed DCR for at least 6 months.

Summary of patients with CR+PR+SD (regardless of duration) will include at least median, range, min, max and patients (n, %) with observed CR+PR+SD.

11.10.3Subgroup Analyses

Not applicable.

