9. INVESTIGATIONAL PLAN

9.1. STUDY DESIGN AND PLAN

This is an open label, multicenter, treatment duration increment trial Phase I runin study followed by two expansion cohorts to evaluate the safety, pharmacodynamic and preliminary antitumor activity of CX-4945 in patients with advanced basal cell carcinoma. All patients will receive CX-4945 until evidence of progression, intolerable toxicities most probably attributable to CX-4945, or withdrawal from the study. Day 1 of the study will be defined as the first day a patient receives CX-4945 (for the list of study assessments, please see the Study Flowchart in Appendix A).

This study population will consist of patients ≥ 18 years old with a histologically confirmed diagnosis of advanced BCC (metastatic BCC [mBCC] or locally advanced BCC as defined as follows) which has progressed on smoothened

inhibitor or that are intolerant to smoothened inhibitor (see Section 10.1.1, Inclusion Criteria).

Patients with mBCC are required to have histologic confirmation of a distant BCC metastasis (e.g., lung, liver, lymph nodes, or bone).

Patients with locally advanced BCC are required to have disease that is considered inoperable or to have a medical contraindication to surgery (see Section 10.1.1, Inclusion Criteria).

Patients with nevoid BCC syndrome (Gorlin syndrome) may enroll in this study but must meet the criteria for locally advanced or metastatic disease listed above.

In the phase I treatment duration increment part of the study, the 28-day continuous dosing of CX-4945 [1000 mg twice daily] will be explored. Dose cohort will initially include a minimum of 3 patients. A standard 3+3 design will be used. If no DLTs are seen in the 3 patients, the treatment duration increment part will be closed and the expansion cohorts will be opened.

If 1 patient out of 3 experiences a dose-limiting toxicity (DLT), up to 3 additional patients will be recruited (for a maximum of 6). If there are < 2/6 patients with DLT, this will be declared the dose for the Recommended Phase II Dose (RP2D), the Phase I will be closed and two expansion cohorts will be opened. If 2 out of 3, or 2 out of 6, patients experience DLT, the previous Phase I oral dosing regimen of 1000 mg BID (total daily dose 2000 mg) for 21 days followed by 7 days of rest will be selected for the expansion cohorts. The expansion cohorts will include 10 patients with locally advanced BCC and 10 patients with metastatic BCC.

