11.2. IDENTITY OF INVESTIGATIONAL PRODUCT

11.3. ADMINISTRATION INSTRUCTION

Patients will receive 1000 mg of CX-4945 twice daily by mouth, beginning on Day 1, and continuously until one of the following occurs:

- Disease Progression:

If the investigator's assessment of progressive disease is equivocal, and in the investigator's opinion the patient is still deriving benefit from treatment, treatment with CX-4945 should be continued, and the patient should be re-evaluated at the next tumor assessment timepoint.

- Intolerable toxicity most probably attributable to CX-4945.
- Withdrawal from the study.

Patients will be instructed to take oral antiemetic prophylaxis at least 1 hour prior to taking the study drug. Other oral medications should be taken at least one hour before or 2 hours after ingesting the dose of CX-4945 capsules.

Patients will take five 200-mg CX-4945 capsules twice daily, two hours after the morning meal and two hours after the evening meal (dinner) with water. Patients are advised to take 1 capsule at a time with a pause in between each. This method may prevent a clumping effected in the stomach, so patient can take as much as 10 minutes to swallow each capsule.

The study drug will be taken on an empty stomach with at least six ounces (180 mL) of water. After CX-4945 administration, all patients will be NPO (except for water) for 2 hours, after which, the patient may eat.

At each study visit, patients will be given enough capsules for dosing until the next study visit. The investigator is required to confirm that any woman of childbearing potential has a negative pregnancy test, understands the teratogenic potential of CX-4945, and is using two forms of acceptable contraception, including one barrier method, prior to dispensing CX-4945.

When CX-4945 capsules are dispensed, each patient will be provided with specific dosing instructions, including the number of capsules to take at each morning and evening dose. The number of containers and capsules being dispensed, the patient number, and the date dispensed will be recorded on the Case Report Form.

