For patients with mBCC, response assessments by the investigator will be categorized as complete response, partial response, stable disease, or progressive disease using RECIST. Objective responses using RECIST should be confirmed on repeat assessments 4 or more weeks after initial documentation of response. The same imaging modality (CT or MRI) used to define measurable disease sites at baseline must be used throughout the study (e.g., the same contrast protocol for CT scans). All patients are required to have imaging of the chest, abdomen, and pelvis; any additional areas imaged during screening (e.g., head or neck, limbs) should also be imaged at each tumor assessment. If the investigator's assessment of progressive disease is equivocal, and in the investigator's opinion the patient is still deriving benefit from treatment, treatment with CX-4945 should be continued, and the patient should be re-evaluated at the next tumor assessment timepoint.

For patients with locally advanced BCC, response assessments by the investigator will be categorized as response, stable disease, or progressive disease using the composite tumor assessment criteria (see Appendix C). Measurements of externally assessable tumor, assessment of tumor ulceration, description of the lesion and any changes since the previous assessment, and digital photography of target lesion(s) will be performed. If the patient has a target lesion(s) containing a RECIST-measurable component by CT or MRI, radiographic assessment is also required and should be incorporated into the response assessment according to Appendix C. If the investigator's assessment of progressive disease is equivocal, and in the investigator's opinion the patient is still deriving benefit from treatment, treatment

with CX-4945 should be continued, and the patient should be re-evaluated at the next tumor assessment timepoint.

f. Tumor Biopsy

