3.2.3. Evaluation of best overall response. The best overall response is the best response recorded from the start of treatment until disease progression/recurrence (taking as reference for progressive disease the smallest measurements recorded since the treatment started). In general, the patient's best response assignment will depend on the achievement of both measurement and confirmation criteria (see Section 3.5.1). Table 1 provides overall responses for all possible combinations of tumor responses in target and nontarget lesions with or without the appearance of new lesions.

² See Appendix I of the Therasse et al. 2000 article.

| RECIST Best Overall Response: Patients with Measurable Disease | | | | | | | | |
|---|--------------------|-------------|-------------------------|--|--|--|--|--|
| Target Lesions | Non-target Lesions | New Lesions | Overall Response | | | | | |
| CR | CR | No | CR | | | | | |
| CR | SD | No | PR | | | | | |
| PR | Non-PD | No | PR | | | | | |
| SD | Non-PD | No | SD | | | | | |
| PD | Any | Yes or No | PD | | | | | |
| Any | PD | Yes or No | PD | | | | | |
| Any | Any | Yes | PD | | | | | |

Table 1. Overall responses for all possible combinations of tumor responses in target and nontarget lesions with or without the appearance of new lesions

CR = complete response; PR = partial response; SD = stable disease; and PD = progressive disease. See text for more details.

Note: If the investigator's assessment of progressive disease is equivocal, and in the investigator's opinion the patient is still deriving benefit from treatment, treatment with CX-4945 should be continued, and the patient should be re-evaluated at the next tumor assessment timepoint.

- Patients with a global deterioration of health status requiring discontinuation of treatment without objective evidence of disease progression at that time should be classified as having "symptomatic deterioration." Every effort should be made to document the objective disease progression, even after discontinuation of treatment.
- In some circumstances, it may be difficult to distinguish residual disease from normal tissue. When the evaluation of complete response depends on this determination, it is recommended that the residual lesion be investigated (fine-needle aspiration/biopsy) before confirming the complete response status.

3.2.4. Frequency of tumor re-evaluation. Frequency of tumor re-evaluation while on treatment is defined in this study as every 8 weeks.

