11.9.1 Primary Efficacy Endpoints

The efficacy endpoints include the following:

• **Best Overall Response**: Assessed separately for patients with mBCC and with locally advanced BCC as a function of radiographic, photographic, and pathologic review (Appendices B, C, G and H of the protocol) as described below.

For patients with mBCC: Overall Response will be assessed using the Response Evaluation Criteria in Solid Tumors (RECIST).

For patients with locally advanced BCC: Overall response will be assessed using a composite response endpoint that incorporates externally visible tumor dimension and tumor ulceration, as well as RECIST for lesions with a RECIST-measurable component.

Patients will be categorized as Complete Response (CR), Partial Response (PR), Stable Disease (SD), Progressive Disease (PD), and Not Evaluable (NE) in Overall Response at each assessment.

• **Objective Response**: Defined as a Complete Response (CR) or Partial Response (PR) in Overall Response determined on two consecutive assessments ≥ 4 weeks apart.

In patients with locally advanced BCC achieving a CR or PR, tumor biopsies will be used in the final determination of CR. CR is defined as absence of residual BCC on biopsy; PR is defined as presence of residual BCC on biopsy.

• Analysis of the changes in *Gli1* expression will be conducted by the OncoCyte Corporation (formerly Insight Genetics) and a separate report will be prepared. Thus detailed analysis is not included in this SAP.

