11.9.2 Other Efficacy Endpoints

- **Progression Free Survival (PFS):** Defined as the time from the date of the first dose of study drug until the date of progressive disease or death from any cause, whichever occurs first. PFS will be censored as follows:
 - Patients who had no event (i.e., they did not die or have PD) will be censored at the date of their last tumor assessment.
 - Patients with no baseline assessment will be censored at the date of the first dose.
 - Patients who started a new anti-cancer therapy prior to documented PD or death will be censored at the last tumor assessment prior to initiation of new anti-cancer therapy.
- **Duration of Response (DOR):** Defined as the time from the date of first documented response (CR or PR) until the date of progressive disease or death from any cause, whichever occurs first, after achieving response. DOR will be censored as follows:
 - Patients who had no event (i.e., they did not die or have PD) will be censored at the date of their last tumor assessment.
 - Patients who started a new anti-cancer therapy prior to documented PD or death will be censored at the last tumor assessment prior to initiation of new anti-cancer therapy.
- **Duration of Stable Disease (DSD):** Defined as the time from the date of first documented Stable Disease (SD) response until the date of progressive disease or death from any cause, whichever occurs first, after achieving SD response. DSD will be censored as follows:
 - Patients who had no event (i.e., they did not die or have PD) will be censored at the date of their last tumor assessment.
 - Patients who started a new anti-cancer therapy prior to documented PD or death will be censored at the last tumor assessment prior to initiation of new anti-cancer therapy.
- **Disease Control Rate (DCR):** Defined as the percentage of patients who have achieved CR, PR, or SD lasting at least 6 months.
- **Duration of Disease Control (DDC):** Defined as the time from the date of first documented response (CR or PR) or Stable Disease (SD) until the date of progressive disease or death from any cause, whichever occurs first, for patients with CR, PR or SD lasting at least 6 months. DDC will be censored as follows:
 - Patients who had no event (i.e., they did not die or have PD) will be censored at the date of their last tumor assessment.

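### SAP 11.10.1 credits a response after progressive disease without limiting it to equivocal progression or setting a matching progression date, so a credited responder can have DOR longer than PFS

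*SAP*

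**What the plan says.** SAP 11.10.1 treats as partial or complete responders "patients who experience progressive disease but continue treatment under the protocol and experience partial or complete response in a subsequent tumor assessment". The sentence does not mention equivocal progression.

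The protocol is narrower:

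- Section 9.1: "All patients will receive CX-4945 until evidence of progression", or until intolerable toxicity or withdrawal.
- Section 11.3 allows dosing to go on when the investigator's "assessment of progressive disease is equivocal" and the patient is still thought to benefit, with re-evaluation at the next assessment. Section 12.1(e) and Appendices B and C repeat this. None of these places says that a later response counts as a response.
- Appendix B, 3.2.3 (RECIST): "The best overall response is the best response recorded from the start of treatment until disease progression/recurrence". Appendix C, for locally advanced BCC, states no such window.

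Neither document has a response category for equivocal PD. In Protocol 12.1(e), locally advanced disease is "categorized as response, stable disease, or progressive disease using the composite tumor assessment criteria". SAP 11.9.1 lists complete and partial response, then "Stable Disease (SD), Progressive Disease (PD), and Not Evaluable (NE) in Overall Response at each assessment".

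Protocol 15.2 and SAP 11.9.1 both require response on two consecutive assessments at least 4 weeks apart.

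SAP 11.9.2 defines PFS as the "time from the date of the first dose of study drug until the date of progressive disease or death from any cause". DOR runs from the first documented response "until the date of progressive disease or death from any cause, whichever occurs first, after achieving response". No censoring rule covers a PD that was later overridden for response. SAP section 12 reports no significant departure from the protocol and does not mention the rule.

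**The concern.** Three things are left unsettled by one sentence in 11.10.1.

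1. **Which PD can be overridden.** As worded, any recorded PD qualifies if the patient stayed on treatment under the protocol. For metastatic BCC that contradicts the Appendix B window.
2. **Whether confirmation applies.** The sentence asks only for a response at one later assessment, while the definition of objective response asks for two.
3. **What the overridden PD means elsewhere.** It is ignored for ORR and CRR, but 11.9.2 does not say whether it is still a PFS event.

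At stake are the response rates and the coherence of the time-to-event outputs. The trial is open label and response is assessed by the investigator, so a rule that can move ORR in only one direction should be tightly defined. Two programmers could both follow the SAP and report different PFS for the same patient.

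**Working it through.** The documents give no figure for this rule, so there is none to reproduce. The check applies the SAP definitions to illustrative patients. The timelines are assumptions, not trial data.

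**Inputs.** Tumour assessments every 8 weeks (Protocol 12.1(e); Appendix B, 3.2.4). Confirmation at least 4 weeks after first response (Protocol 15.2; SAP 11.9.1). PFS and DOR as defined in SAP 11.9.2.

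**Formulas, in weeks from first dose.** Let p be the first PD, r the first response (r later than p), and d the PD after the response.

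- First PD kept as an event: PFS = p.
- First PD disregarded: PFS = d.
- DOR = d − r under either reading, because DOR looks only at PD after the response.
- So when the first PD is kept, DOR exceeds PFS whenever d − r > p.

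**Results.** All responses are taken as confirmed.

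| Sequence | PFS, first PD kept | PFS, first PD disregarded | DOR |
|---|---|---|---|
| PD 8, PR 16, PD 40 | 8 | 40 | 40 − 16 = 24 |
| PD 8, PR 16, PD 32 | 8 | 32 | 32 − 16 = 16 |
| PD 8, PR 16, PD 24 | 8 | 24 | 24 − 16 = 8 |
| SD 8, PD 16, PR 24, PD 48 | 16 | 48 | 48 − 24 = 24 |
| PR 8, PD 24 (ordinary responder) | 24 | not applicable | 24 − 8 = 16 |

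DOR exceeds PFS in rows 1, 2 and 4, and equals it in row 3. An ordinary responder never shows the anomaly. It is therefore possible only for patients credited after PD, and even then not inevitable.

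**Direction of the effect on ORR and CRR.** The Appendix B window counts responses before progression. The SAP sentence adds responses after it and removes none. The numerator can only rise or stay the same, and the denominator does not change.

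**Weight of one credited patient.** Assume 10 locally advanced expansion patients (the planned number), the 2 metastatic expansion patients reported in SAP section 6, and 3 to 6 run-in patients whose split by disease is unknown.

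- Locally advanced, n = 10 to 16: 1/10 = 10.0 to 1/16 = 6.25 percentage points.
- Metastatic, n = 2 to 8: 1/2 = 50.0 to 1/8 = 12.5 points.
- Overall, n = 15 to 18: 1/15 = 6.7 to 1/18 = 5.6 points.

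These are illustrations, not bounds. SAP section 7 can exclude patients from the Efficacy population, Protocol 10.4 can add replacements, and the SAP does not state how many locally advanced patients were actually enrolled.

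**The case against.** The strongest reply is that the sentence covers only patients who stay on treatment under the protocol. Since the protocol's only stated route past progression is an equivocal assessment, equivocal PD is very likely what was meant. Appendix B prints its equivocal-PD note directly under the best-response table, so re-evaluation belongs to that scheme. On this reading the conflict with the Appendix B window largely falls away. If an equivocal PD that resolves is also not PD for PFS, the first row gives PFS 40 and DOR 24, with no anomaly.

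Much of this stands. It does not settle the point, because the SAP states neither step. Even if only equivocal PD is meant, 11.9.2 does not say whether an overridden PD is a PFS event, and 11.10.1 still does not say whether the response must be confirmed.

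Two further replies are fair. SAP 10.1 already requires by-subject listings that include response status, so a PD followed by a response would be visible. The omission from section 12 is minor, because a rule that only implements the equivocal-PD provision is closer to detail than to change.

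Stronger readings are tempting but not supported:

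- *The rule breaches the protocol's response criteria in both disease groups.* Appendix C sets no best-response window, so the conflict in the text is confined to metastatic BCC.
- *The duration of CR, PR or SD could come out negative.* The wording of that endpoint does not carry the after-response phrase, but a time from response until PD cannot sensibly end before it starts.
- *The rule was added to improve the results.* The SAP was written when early termination was known, but nothing in the documents speaks to motive or to what was seen.

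**Conclusion.** The point holds in a limited form. SAP 11.10.1 states a rule broader than the protocol provision it appears to rest on. Read literally, the rule conflicts with Appendix B for metastatic BCC, and it has no matching progression date in 11.9.2. The result is an upward-only effect on ORR and CRR compared with the Appendix B window, and PFS of either 8 or 40 weeks beside a DOR of 24 in the illustrative case.

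A reader might infer that the reported ORR is inflated, or that the judgement against the 5% no-interest rate is affected. The documents do not show either: the number of patients who depend on the rule is unknown and may be zero. Response is a secondary outcome in the protocol, results are descriptive with no formal testing (SAP 10.1 and 10.5), and the RP2D is unaffected. Severity is minor to should-fix. The size rests on assumed timelines and on assumed patient numbers by disease group.

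**What to change.** 1. **SAP 11.10.1.** Credit a response after PD only if that PD was recorded as equivocal, re-evaluation did not confirm it as PD, and the confirmed objective response criteria of 11.9.1 are met.
2. **SAP 11.9.2.** Use one PD date for ORR, CRR, PFS, DOR and the other duration endpoints. Disregard an equivocal PD for all of them if the next evaluable assessment before any new anti-cancer therapy is CR, PR or SD. Otherwise date PD at the first equivocal assessment for all of them. A credited response then falls after first dose and before the single PD date, so DOR cannot exceed PFS. If the week-8 PD in the first row was equivocal, PFS is 40 and DOR is 24.
3. **Strict analysis.** Also report ORR and CRR counting only responses before the first recorded PD. Appendix B requires this for metastatic BCC; for locally advanced BCC it is a sensitivity analysis. In the listing already planned under SAP 10.1, flag each responder who depends on the rule.
4. **Fallback.** If equivocal PD cannot be identified in the data, make the strict analysis the main one. Show the post-PD credit for ORR and CRR only, as a sensitivity analysis.
5. **SAP section 12.** Mention the rule.

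The cost is a few sentences, one extra ORR and CRR output, and a flag in an existing listing. ORR may be slightly lower. Neither document describes a field for equivocal PD, so some data queries may be needed; the fallback needs no new data. The change concerns the analysis only and does not affect who continues treatment.

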6. SAMPLE SIZE DETERMINATION

In the treatment-duration-increment part of the study, a 3+3 study design will be utilized, therefore approximately 3-6 patients will be enrolled to define the RP2D.

In the expansion part of the study, a total sample size of 20 patients is proposed; 10 patients with local advanced BCC and 10 patients with metastatic BCC. Assume that CX-4945 is of no interest if its true response is 5% or lower, the proposed sample size for each sub-population will provide an 80% confidence interval of (5.5%, 45.0%) given that there are 2 responses out of the 10 patients. This would provide adequate evidence to suggest that additional studies with this agent may be warranted.

10 patients with metastatic BCC were planned in the expansion part of the study, but only 2 were enrolled due to early termination.

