7. ANALYSIS POPULATIONS

The following analysis sets/populations will be used in this trial:

- **Safety population:** All enrolled patients who receive any amount of study drug. Unless otherwise noted, all safety analyses will be performed using Safety population.
- **Dose determining population:** All patients treated in the Phase 1 treatment-durationincrement part of the study. The dose determining population will be used to determine the primary outcome of the study, the RP2D dose.
- Efficacy population: All patients who are treated in the treatment-duration-increment cohort or the expansion cohort and whose pathologist's interpretation of baseline biopsy is consistent with BCC. Patients without interpretable baseline tissue, as determined by the pathologist, or by pathology report from the study site documenting a pathologist's determination of BCC will be excluded from the Efficacy population. Such patients' efficacy data will be presented in by-subject listings but excluded from all summary analyses. Objective response will be assessed separately for patients with mBCC vs. locally advanced BCC.
- **Relative Dose Intensity (RDI) population:** All patients treated in the expansion cohort including those who complete the protocol-defined treatment or discontinue treatment due to adverse events or for disease progression. Patients who are discontinued for any reason other than for adverse events or for disease progression will not be included in the relative dose intensity assessment. The RDI population will be used for the assessment of relative dose intensity defined for each cycle.

For some objectives (pharmacodynamics, biomarker parameters) a subgroup of patients of the efficacy population with respective baseline and post-baseline measurements will be used as described in section 11.9.1 below.

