9. INTERIM ANALYSIS

No interim analysis is planned for this study.

10.DATA CONVENTIONS FOR ANALYSIS

10.1General Statistical Principles

All statistical processing will be performed using SAS® unless otherwise stated. Any statistical tests will be two-tailed at significance level of 0.05 unless otherwise specified.

All observed and derived variables (e.g., change from baseline, percentage change from baseline, and response status) used in the summaries of analyses will be presented in by-subject listings. Unless otherwise noted, the data will be sorted first by treatment assignment, then by subject number and then by date within subject number.

Efficacy and safety results will be summarized descriptively. Categorical parameters will be summarized by the number and percentage of subjects in each category. Denominators for percentages will be appropriate to the purpose of the analysis. Percentages will typically be presented to one decimal (Note: 0% and 100% will be in integer format). Continuous parameters will be summarized as number of subjects, mean, standard deviation (SD), median, minimum, and maximum.

10.2Study Day

Day 1 is defined as the date of first study drug administration. Study day is calculated relative to the date of Day 1. For subjects who did not have a recorded date of first study drug administration, study day will not be calculated.

10.3Baseline and Change from Baseline

Baseline is defined as the last non-missing assessment prior to the first administration of study drug. Change from baseline is defined as post-baseline value minus baseline value unless otherwise specified. Percent change from baseline is (Change from baseline / Baseline) * 100%.

10.4Analysis Visit Window

Results will be summarized according to the visit as recorded in the eCRF. No visit windows will be applied.

10.5Multiple Comparisons

Not applicable. There will be no formal hypothesis testing.

11.STATISTICAL EVALUATION

11.1Subject Disposition

The number and percentage of subjects screened, enrolled, included in key analysis populations, completing the study, and withdrawing from the study (together with the reasons for withdrawal) will be summarized using frequencies and percentages, overall and by cohort (treatment-duration-increment, expansion).

A by-subject listing will show all subjects enrolled and their disposition.

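### The confidence interval specified for ORR and CRR collapses to ±1/(2n) when there are no responders, in groups as small as these (0/10: −5% to 5%, exact 0% to 30.8%)

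*SAP*

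**What the plan says.** SAP 11.10.1 defines ORR as confirmed responders divided by the number of patients in the Efficacy population, reported overall and separately for metastatic (mBCC) and locally advanced disease. The interval is specified in one sentence: "A continuity-corrected 95% confidence interval based on the normal approximation will accompany each ORR". The next sentence extends it: "Complete response rates (CRR) will be summarized in parallel fashion to ORR". Nothing is said about small denominators, zero responders, or limits outside 0–100%. Protocol 15.2 names no interval method, so the SAP sentence governs.

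Other provisions bear on the point:

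- **Denominator.** SAP 7 builds the Efficacy population from "All patients who are treated in the treatment-duration-increment cohort or the expansion cohort", subject to a baseline biopsy consistent with BCC.
- **Group sizes.** SAP 6 gives 3–6 run-in patients and 10 planned per expansion cohort, and says of the mBCC expansion cohort "but only 2 were enrolled due to early termination".
- **Non-responders.** SAP 11.10.1 adds "Patients without at least one post-baseline response assessment will be treated as non-responders".
- **Complete response in locally advanced disease.** SAP 11.9.1: "CR is defined as absence of residual BCC on biopsy".
- **Design figure.** SAP 6 (and protocol 15.6): "the proposed sample size for each sub-population will provide an 80% confidence interval of (5.5%, 45.0%) given that there are 2 responses" out of 10.
- **Role.** SAP 10.5: "There will be no formal hypothesis testing".

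**The concern.** The normal approximation is poor for a proportion when n is small and the count is near 0 or n, and those are the conditions here. With no responders the estimated variance is zero, and the interval consists of the continuity correction alone. Its width then reflects only n and bears no relation to the rates the data can exclude.

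Zero counts are realistic. Patients with no post-baseline assessment count as non-responders, and a complete response in locally advanced disease needs a biopsy free of residual tumour, so CRR is even likelier than ORR to be zero in a group.

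What is at stake is how the activity result is read. With 0/10, the SAP interval would suggest that rates above 5% are excluded. That 5% is also the plan's own no-interest rate, so the interval would look like clear evidence of inactivity. Ten patients without a response are compatible with rates up to about 31%.

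**Working it through.** **Inputs.** Method and level: SAP 11.10.1. Run-in 3–6, 10 planned per expansion cohort, 2 mBCC expansion patients enrolled: SAP 6. The number enrolled in the locally advanced expansion cohort and the disease split of the run-in are not stated. *Assumption:* 10 locally advanced expansion patients, and 3–6 run-in patients split in any way. Then locally advanced n = 10–16, mBCC n = 2–8, and overall n = 15 (10+2+3) to 18 (10+2+6).

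**Formulas.**

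- SAP interval, read as continuity-corrected Wald: p ± [1.96·√(p(1−p)/n) + 1/(2n)], p = x/n.
- Exact (Clopper-Pearson) 100(1−α)% limits: lower = the α/2 quantile of Beta(x, n−x+1); upper = the 1−α/2 quantile of Beta(x+1, n−x). At x = 0 the 95% upper limit reduces to 1 − 0.025^(1/n).
- Coverage: the binomial probability of all counts whose interval contains the true rate.

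**Step 1: the plan's own figure.** For 2/10 at 80%:

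| Method | 80% interval |
|---|---|
| Exact (Clopper-Pearson) | 5.45% to 44.96% |
| Wald | 3.8% to 36.2% |
| Wald, continuity-corrected | −1.2% to 41.2% |
| Wilson | 8.6% to 39.8% |
| Wilson, continuity-corrected | 5.6% to 45.2% |

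Only the exact method gives the stated 5.5% to 45.0%. The design figure is therefore exact and the analysis interval is not. At the same 80% level the analysis method puts the lower limit for 2/10 below zero.

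**Step 2: zero responders.** With p = 0 the square root is 0, so the interval is ±1/(2n). For n = 10, 1/(2n) = 1/20 = 5%; exact upper limit 1 − 0.025^(1/10) = 30.8%.

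| n | SAP upper limit | Exact upper limit |
|---|---|---|
| 2 | 25.0% | 84.2% |
| 8 | 6.3% | 36.9% |
| 10 | 5.0% | 30.8% |
| 13 | 3.8% | 24.7% |
| 15 | 3.3% | 21.8% |
| 16 | 3.1% | 20.6% |
| 18 | 2.8% | 18.5% |

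Setting the negative lower limit to 0 leaves the upper limit unchanged.

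**Step 3: other counts (95%).**

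| Count | SAP interval | Exact interval |
|---|---|---|
| 1/10 | −13.6% to 33.6% | 0.3% to 44.5% |
| 2/10 | −9.8% to 49.8% | 2.5% to 55.6% |
| 1/2 | −44.3% to 144.3% | 1.3% to 98.7% |
| 2/2 | 75% to 125% | 15.8% to 100% |

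For 2/10: 1.96·√(0.2·0.8/10) = 0.248, plus 0.05 = 0.298, and 0.20 ± 0.298 gives the limits shown. The last row is the same collapse at the other boundary.

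**Step 4: coverage of the nominal 95% SAP interval.**

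| n | True ORR 10% | 15% | 20% |
|---|---|---|---|
| 10 | 65.0% | 80.2% | 88.6% |
| 13 | 74.5% | 87.2% | 93.8% |
| 16 | 81.1% | 92.0% | 96.5% |
| 10, exact limits | 98.7% | 99.0% | 99.4% |

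The probability of 0/10 at these rates is 34.9%, 19.7% and 10.7%. At n = 10 and a true rate of 10%, non-coverage is 100 − 65.0 = 35.0%, so the zero-responder case accounts for nearly all of it.

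The shortfall starts just above 1/(2n). At n = 10 and a true rate of exactly 5% coverage is close to 100%; at 5.1% it is 40.7%. At n = 2 coverage is still 99.0% and 96.0% at true rates of 10% and 20%, and falls to 42.0% at 30%.

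**The case against.** - **Another formula may be meant.** The sentence names no formula, and a continuity-corrected Wilson interval also rests on the normal approximation. It gives 0% to 34.5% for 0/10 and 0% to 80.2% for 0/2, with no collapse. This is fair as far as it goes, but the SAP does not name Wilson and the ordinary reading is Wald. If Wilson was intended, the sentence still needs to say so.
- **Undercoverage is not general.** This stands. It depends on n and begins just above 1/(2n). At or below the 5% no-interest rate with n = 10, and at rates up to 20% with n = 2, there is none. It is substantial at n = 10 for rates of 10–20% and fades by n = 16 at 20%.
- **The group sizes are not firm bounds.** This also stands. Replacement under protocol 10.4 can add patients to the denominator, baseline-biopsy exclusions can remove them, and the locally advanced count is not given. The collapse to ±1/(2n) occurs at any n.
- **Design and analysis intervals need not match.** True: no decision rule uses either one, and the 2/10 reading in SAP 6 also depends on its 80% level. The mismatch is a secondary observation.
- **ORR is descriptive, and responses are listed by patient.** A reader could recompute the limits, and −44% to 144% is visibly impossible. But 0% to 5% after truncation looks plausible and would mislead.
- **Exact limits are conservative.** Correct. A properly specified score interval would also remove the collapse, so Clopper-Pearson is one valid choice; it matches the method behind the design figure.

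**Conclusion.** The concern holds. Under the Wald reading, the interval that SAP 11.10.1 prescribes for ORR and CRR is invalid at zero responders for every group size considered. Its upper limit runs from 2.8% (n = 18) to 25% (n = 2), where exact limits run from 18.5% to 84.2%. At low non-zero counts its lower limit is negative. At n = 10 its coverage is 65–89% for true rates of 10–20%.

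The collapse itself needs no assumption about enrolment. The listed group sizes assume 10 locally advanced expansion patients and an unrestricted run-in split, before any replacements or biopsy exclusions.

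The RP2D determination is unaffected and no formal test depends on the interval. This should be fixed because it is the only stated measure of uncertainty for ORR and CRR, and a zero-responder group would be reported with far too much certainty.

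**What to change.** In SAP 11.10.1, replace the interval sentence with: *Exact (Clopper-Pearson) 95% confidence intervals will accompany each ORR and CRR.* Naming CRR removes any doubt about what parallel handling covers. Optionally, show the exact 80% interval as well, so that the result can be read against the figure in SAP 6. No responder threshold should be added.

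The cost is one SAP sentence and one SAS option for exact binomial limits; no new data are needed. Some intervals become wider, most clearly at zero responders, and coverage will exceed the nominal level (about 99% at n = 10 for true rates of 10–20%).
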